Aim 1: Investigate the efficacy of iCBT among Black and Latinx IBD patients with elevated psychological distress

We predict that compared to those who receive digital mood tracking, patients who are allocated to iCBT will have (a) lower psychological distress, as measured by the National Institutes of Health (NIH) Patient Reported Outcomes Measurement Information System (PROMIS) anxiety and depression scores and NIH Toolbox Perceived Stress Scale scores, (b) higher HRQoL on overall PROMIS-29 scores and (c) lower disease activity, as measured by patient-reported disease activity indices.

Aim 2: Evaluate implementation of iCBT among Black and Latinx IBD patients

We predict that (a) behavioral factors, such as elevated psychological distress, high self-efficacy, coping, and spirituality will be the strongest predictors of acceptance of iCBT and that other factors such as younger age, higher educational attainment, recent IBD diagnosis, and high disease activity will be associated with higher iCBT use and (b) modifiable individual and process level barriers and facilitators of iCBT use will be identified.

Participants will have IBD and elevated psychological distress and be recruited from the two outpatient clinical sites where the research physician and senior key personnel practice. The total estimated IBD population with clinical visits at Einstein/Montefiore is approximately 1,200 patients. In an average week, about 34 unique IBD patients receive care at one of the two study sites of which about 19% are Black and 30% are Latinx. About 85% have internet access, using active patient portal registration in the electronic medical record as a rough proxy. Based on estimates from the literature, the prevalence of anxiety or depression in IBD is around 20% and up to 66% with active disease.⁸ Thus, we estimate that on a weekly basis at least 6 and up to 22 Black or Latinx IBD patients attending a study site will have elevated anxiety or depression.

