various health insurance plans. The cost for individuals who do not qualify for health insurance coverage will come from the study budget. Participants will be instructed to export from the app a weekly data use report to the research physician's Montefiore email. The research physician will be linked to participant usage and progress through the app. There is an emergency resources section within the app that includes information on crisis help-lines and other resources for users in emergency situations. The app is available for use in iOS and Android systems as well as online through any web browser. App content is available in English with text translations in Spanish.

All participants will receive a unique link to complete a follow-up questionnaire at 48 weeks post intervention (Table 1). Non-responders will receive a reminder phone call twice weekly for 2 weeks and thereafter be considered lost to follow-up.

Table 1. Timeline and Sources of Data		
Baseline - REDCap Questionnaire (completed by patient at office visit or remotely)		
Socio-demographics	Assessment Tools	Clinical features

 ▪ Age ▪ Race/ethnicity ▪ Sex ▪ Birthplace ▪ Primary language ▪ Educational attainment ▪ Employment status ▪ Health insurance ▪ Marital status 	
 ▪ IBD disease activity index: Short Crohn's Disease Activity Index for Crohn's disease or Simple Clinical Colitis Activity Index for ulcerative colitis ▪ PROMIS-29 ▪ Perceived Stress Scale ▪ PROMIS Self-efficacy Managing Emotions ▪ PhenX Toolkit – Spirituality ▪ Brief Resilient Coping Scale 	
 ▪ IBD phenotype ▪ Disease duration ▪ IBD medications ▪ Previous/current psychiatric diagnosis, suicidal ideation or hospitalization
Follow-up at 84 weeks REDCap Questionnaire (completed by patient remotely)		
	Assessment Tools	
	
 ▪ IBD disease activity index: Short Crohn's Disease Activity Index for Crohn's disease or Simple Clinical Colitis Activity Index for ulcerative colitis ▪ PROMIS-29 ▪ Perceived Stress Scale ▪ PROMIS Self-efficacy Managing Emotions 	

3) Study Population

We aim to recruit 25 patients in each study arm for a total of 50 participants. Eligibility will be restricted to:

- age \geq 18 years
- race/ethnicity self-identified as Black/African American or Hispanic/Latinx
- established diagnosis of Crohn's disease or ulcerative colitis

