In the event in-person visits are not possible, patients will be recruited at the time of a telemedicine visit and asked the same initial screening questions to confirm eligibility. The informed consent process would take place over the telephone (see next section for details), and patients will be sent a unique link to the REDCap survey. Patients completing the questionnaire outside of an in-person visit will access and complete it on their own personal device. The research physician will receive a daily report of newly completed questionnaires to ensure adequate follow-up. Patients with severe psychiatric distress or suicidality will be linked to psychiatric services at Montefiore. The research physician/assistant will inform patients of their eligibility to be randomized into the trial.

5) Informed Consent

Patients eligible for inclusion in the trial after confirmation of initial screening factors (age, race/ethnicity, diagnosis of IBD, internet access) will undergo an informed consent process using the attached consent form that includes discussion of study procedures, risks and benefits. The research physician/assistant will perform the informed consent process at the time of an office visit. If in-person office visits are not possible, patients will receive a copy of the informed consent form (emailed) in advance of the informed consent process, which would be conducted over the telephone by the research physician/assistant.

Participants may receive a total of \$40 for completing the two study questionnaires. They will receive a \$20 gift card for completing a questionnaire at the beginning of the study and another \$20 gift card if they complete a questionnaire at the end of the study.

6) Risk/Benefit

Risks of the study include a loss of confidentiality or privacy. Only the research study team will have access to study related documents and participants questionnaires. Study documents in a paper form will be stored in a study binder in a locked cabinet in the research physician's office and accessed only by the research team. Study documents in digital form will be password protected and accessed only by the study team. Study questionnaires will be stored on the secure password protected online platform REDCap. Only the study team will have REDCap access to the study questionnaires.

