Other risks of the study are the risk of discomfort or distress answering questions about mental health and discomfort or distress addressing mental health through a digital platform. It will be made clear to participants that they may choose not to answer any questions they feel uncomfortable with and that use of the iCBT application is completely voluntary. Participants are also directed to seek immediate medical attention in case of any severe psychological distress e.g. suicidality. The research physician will have a password-protected provider interface to the iCBT platform that enables aggregate information regarding individual participant iCBT data usage.

7) Data Analysis

Aim 1: Investigate the efficacy of iCBT among Black and Latinx IBD patients with elevated psychological distress

The primary outcome will be the level of psychological distress (scores in the domains of anxiety and/or depression on the PROMIS-29 assessment tool) at 84 weeks between study arms. PROMIS-29 is a 29-item form that includes 4 questions in each of the domains of anxiety and depression.¹⁶ Higher scores indicate a greater level of the measured trait, and raw scores are converted to a T-score that centers at a mean of 50 with a standard deviation of 10 in the general population. The minimum clinically significant change in the domains of anxiety and depression has been shown to be 2.3-5.5 points.^{17,18} The other PROMIS-29 domains of physical function, fatigue, sleep disturbance, ability to participate in social roles, pain intensity and interference together give a measure of HRQoL.

Secondary outcomes will be the change in perceived stress, overall HRQoL and IBD disease activity. Perceived stress will be measured with the 10-item Perceived Stress Scale. Like PROMIS-29, higher scores indicate a higher level of the measured trait, and raw scores are converted to a T-score. The overall HRQoL will be measured with the PROMIS-29 including the non-anxiety/depression domains. Disease activity will be measured by the Short Crohn's Activity Index (for participants with Crohn's disease) or Mayo sub-scores (for participants with ulcerative colitis).

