Primary analysis will be by intention-to-treat with participants analyzed in the group to which they were randomized. We will use descriptive statistics to summarize socio-demographic and disease characteristics of both study groups and of app usage in the iCBT group: number of modules completed; weekly time spent on app; participation in community support groups. Our primary hypothesis is that participants in the iCBT group will have lower psychological distress scores compared to those in the digital mood tracking group post-intervention. To test the association between psychological distress (T-score for anxiety, depression) and study group, we will use Student's t-test if the normality assumption is met, or the Mann-Whitney U test if normality is appreciably violated. Assuming a minimum clinically significant change of a 5.5 points difference in T-scores between study groups with a standard deviation of \pm 6 points, a sample size of 40 participants (20 in each arm) will be needed to have 80% power at an alpha of 0.05. Targeting a recruitment sample size of 50 participants (25 in each arm) would allow for roughly 20% drop-out rate.

Our secondary hypotheses are that participants in the iCBT group will have lower perceived stress scores and higher HRQoL. To test these hypotheses, we will again use Student's t-test if the normality assumption is met or the Mann-Whitney U test if normality is appreciably violated. Finally, we hypothesize that elevated disease activity at baseline (Short Crohn's Disease Activity Index \geq 150 or Mayo sub-scores \geq 2) will be associated with achieving a minimum clinically significant change in T-score. To test the association between high baseline disease activity and minimum clinically significant change (as a dichotomous outcome), we will perform Chi-squared or Fisher's exact test.

Aim 2: Evaluate implementation of iCBT among Black and Latinx IBD patients

Participants randomized to iCBT will complete a survey as part of their follow-up assessment at 84 weeks to evaluate their acceptance of and satisfaction with iCBT.

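### The only follow-up questionnaire is closed out after at most four reminder calls in two weeks, with no late window or fallback collection stated for the primary outcome

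*Combined protocol and SAP*

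**What the plan says.** Section 2 (Study Design) sends every participant a link to one follow-up questionnaire, which Table 1 lists as completed remotely by the patient. The rule for people who do not answer is: "Non-responders will receive a reminder phone call twice weekly for 2 weeks and thereafter be considered lost to follow-up".

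Section 5 pays for two questionnaires, one at the start and one at the end, so there is a single post-baseline measurement. Section 7, Aim 1 takes the primary outcome from it (the time point is in weeks): "The primary outcome will be the level of psychological distress (scores in the domains of anxiety and/or depression on the PROMIS-29 assessment tool) at 84". The instrument is short: "PROMIS-29 is a 29-item form that includes 4 questions in each of the domains of anxiety and depression", so eight items carry the primary outcome. The iCBT app has weekly progress assessments, but these are not described as PROMIS-29 and have no stated counterpart in the control arm.

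The primary test is a t-test, or a Mann-Whitney U test, on post-intervention scores under intention-to-treat. No method for missing scores is given. On sample size, section 7 needs 40 evaluable participants and recruits 50, which "would allow for roughly 20% drop-out rate".

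Two further places matter. Section 7, Aim 2 lets participants complete the post-intervention survey at the study site or elsewhere, but that survey is given to the iCBT arm. The follow-up time is 48 weeks post intervention in the text of section 2, and 84 weeks in Table 1 and section 7.

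**The concern.** Both candidate tests use only participants with an observed follow-up score. With one post-baseline measurement, a participant closed out under this rule contributes nothing to the primary comparison. The intention-to-treat statement cannot be met for that person, and there is no intermediate score to support imputation.

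After a follow-up of about a year or more, a 14-day limit saves little. Much of what a longer effort needs is already in the plan: staff place the calls, and baseline can be completed on a study-site computer.

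Two things are at stake. Precision suffers if loss exceeds the allowance. The comparison may also be biased, because people with elevated distress who leave a link unanswered may differ from those who respond, and may differ in one arm more than in the other.

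**Working it through.** **Inputs.** From section 7, Aim 1: difference 5.5 T-score points, SD 6, alpha 0.05, power 80%, 20 evaluable per arm, 25 recruited per arm, about 20% drop-out. From section 2: calls twice weekly for 2 weeks, so 2 × 2 = 4 calls at most; about 34 unique IBD patients a week at the two sites; about 1,200 IBD patients at the institution.

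**1. The plan's own figure.** Normal approximation: n per arm = 2 × (1.960 + 0.842)² × (6/5.5)² = 2 × 7.85 × 1.19 = 18.7, so 19. The two-sided t-test gives 19.69, so 20 per arm, which matches. A one-sided t-test would need only 16, so the stated figure is two-sided. Drop-out: 40/(1 − 0.20) = 50, which matches.

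**2. Power by number evaluable.** Two-sided t-test, noncentrality (5.5/6) × √(n/2), 2n − 2 degrees of freedom:

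| Evaluable per arm | Loss from 25 | Noncentrality | Power |
|---|---|---|---|
| 25 | 0% | 3.24 | 88.8% |
| 24 | 4% | 3.18 | 87.5% |
| 22 | 12% | 3.04 | 84.4% |
| 20 | 20% | 2.90 | 80.6% |
| 19 | 24% | 2.83 | 78.5% |
| 17 | 32% | 2.67 | 73.6% |
| 15 | 40% | 2.51 | 67.9% |

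The 20% allowance is used up at 20 per arm, and one further loss per arm takes power below 80%.

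**3. What recovery could gain.** The documents give no non-response or recovery rate, so both are assumed here. Evaluable n = 25 × [1 − loss × (1 − share recovered)], with fractional n kept:

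| Loss before recovery | None recovered | A quarter | Half |
|---|---|---|---|
| 10% | 85.2% | 86.2% | 87.1% |
| 20% | 80.6% | 83.1% | 85.2% |
| 30% | 74.9% | 79.3% | 83.1% |
| 40% | 67.9% | 74.9% | 80.6% |
| 50% | 59.3% | 69.8% | 77.9% |

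At the planned 20% loss (five per arm), recovering two per arm gives 22 per arm and 84.4%, a gain of 84.4 − 80.6 = 3.8 percentage points.

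**4. Bias.** If a fraction L of an arm is missing and those people score m points worse than the observed ones, the observed arm mean is off by L × m. For an assumed L of 20% to 40% and m of 3 to 6 points, this runs from 0.20 × 3 = 0.6 to 0.40 × 6 = 2.4 points, against a target difference of 5.5. The same pattern in both arms would cancel; a pattern in one arm only passes straight into the comparison.

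**5. How far clinic visits would help.** Over six weeks, 34 × 6 / 1,200 = 17%, or 5 × 0.17 = 0.85 of five non-responders per arm. This is rough. The 1,200 covers the whole institution, repeat visits are counted again, and sicker patients may attend more often.

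**The case against.** A limit of two weeks and four calls in a 50-person trial is a defensible operational choice. The plan budgets for 20% loss, so gains from recovering participants within that allowance are power above the 80% target. Participants are paid for the end questionnaire, and the control arm is offered iCBT after the post-intervention assessment; both encourage response. All of this stands, with one qualification: the iCBT offer acts on the control arm only, so it could itself make response differ between arms.

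A reader might infer more than the text supports:

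- **That staff reach these people by phone.** Section 2 says only that reminder calls are made. Some of those still silent may never pick up, and a phone script would not help them.
- **That they will soon be seen in clinic.** Participants are "recruited from the two outpatient clinical sites where the research physician and senior key personnel practice", which describes recruitment. No follow-up visit is scheduled, and the plan's own figures suggest roughly 17% attendance in six weeks.
- **That outcomes are thrown away.** Nothing says the link closes or that a late questionnaire is refused. The sentence can be read as ending active pursuit only.
- **That the trial has no spare size.** The 20% allowance contradicts this.

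The on-site option under Aim 2 is a partial answer at most. It is stated for the iCBT arm's survey and does not extend the two weeks. If only that arm has it in practice, ascertainment could differ between arms.

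**Conclusion.** The point holds as a matter of follow-up procedure. The rule ends pursuit of the sole post-baseline source of the primary outcome after at most four calls in two weeks, and nothing is stated about late or alternative collection.

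For power, the planned allowance covers loss up to 20%; the deficit appears only beyond it (78.5% at 24% loss, 73.6% at 32%). These figures assume the plan's 5.5 points and SD 6 with a two-sided t-test. For bias, there is no safe loss rate if non-response is selective and differs by arm; the 0.6 to 2.4 points is an assumed illustration, not a forecast.

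The documents do not show that collectable outcomes are being discarded or that the trial is underpowered as planned. The benefit of a change depends on a recovery rate nobody has stated. The change is still worth making because it is cheap and specific.

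**What to change.** In the follow-up paragraph of section 2:

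- Replace the two-week cut-off with a fixed response window, for example 6 weeks from the due date. Keep the link open throughout, and allow completion at the study site, on identical terms in both arms.
- Record the date and mode of completion. Include every response received in the window in the primary analysis, and count as lost only those with no score at its end.
- As an optional last resort, take the eight anxiety and depression items by scripted phone call. Offer this equally in both arms, using staff unaware of allocation where existing staffing allows.

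In section 7, add a sensitivity analysis for late or phone responses. It should supplement the primary analysis, because leaving those people out of the primary analysis would restore the selective missingness. State that the on-site option applies to the follow-up questionnaire in both arms.

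Reconcile the 48-week and 84-week follow-up times across section 2, Table 1 and section 7; until then the window has no defined start.

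The cost is protocol wording, plus a few staff minutes per call if the phone option is used. The downside is a small spread in timing and mode. Phone collection of self-reported distress may also add interviewer effects, which is why it comes last.

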- elevated psychological distress: at least one T-score within two standard deviations above the mean in the domains of anxiety or depression on the National Institutes of Health Patient Reported Outcomes Measurement Information System-29 (PROMIS-29) with or without a T-score within two standard deviations above the mean for perceived stress on the National Institute of Health Toolbox Perceived Stress Scale (Perceived Stress Scale)
- internet access (smartphone/mobile device with data plan, computer with internet)
- ability to provide informed consent in English or Spanish

Exclusion criteria are:

- PROMIS-29 anxiety or depression T-scores in the severe range (above 2 standard deviations)
- Current suicidal ideation, past suicidal attempt or hospitalization

4) Participant Recruitment

Recruitment will be active and occur during in-person study site visits. If in-person visits are not possible (e.g. ongoing public health crisis), recruitment will occur via telemedicine visits. All IBD patients will be invited to participate. We anticipate enrolling 1-2 participants weekly into the trial.

For patients recruited during an in-person visit, the research physician/assistant will approach patients during their visit who meet the screening questions (based on age, race/ethnicity, diagnosis of IBD, internet access) to confirm eligibility. After the informed consent process, patients will complete a study questionnaire via a REDCap survey on a study site computer. Responses to this initial questionnaire will determine eligibility for randomization into the study based on the inclusion/exclusion criteria. Upon completion of the questionnaire, computer-automated scores will be generated. Patients with severe psychiatric distress or suicidality will be linked to psychiatric services at Montefiore. The research physician/assistant will inform patients of their eligibility to be randomized into the trial.

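### The primary outcome is anxiety and/or depression with no rule for combining the two domains, while the sample size covers a single test

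*Combined protocol and SAP*

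**What the plan says.** Section 7 (Data Analysis, Aim 1) gives the primary outcome as psychological distress, meaning "scores in the domains of anxiety and/or depression on the PROMIS-29 assessment tool". The same section states one hypothesis that names no domain: "Our primary hypothesis is that participants in the iCBT group will have lower psychological distress scores". The analysis sentence then lists both domains, "To test the association between psychological distress (T-score for anxiety, depression) and study group", using a t-test or a Mann-Whitney test.

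The sample size uses one difference (5.5 points), one SD (6) and one alpha: "a sample size of 40 participants (20 in each arm) will be needed to have 80% power at an alpha of 0.05". On attrition it says: "Targeting a recruitment sample size of 50 participants (25 in each arm) would allow for roughly 20% drop-out rate".

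Two other places bear on the point. Aim 1 in section 2 predicts lower "anxiety and depression scores and NIH Toolbox Perceived Stress Scale scores", which joins the domains with 'and' but also includes perceived stress, a secondary outcome in section 7. Section 3 admits participants with "at least one T-score within two standard deviations above the mean in the domains of anxiety or depression", so a participant may be elevated in only one domain.

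No section says which domain leads, whether one or both must differ, whether the scores are combined, or how two tests share the 0.05.

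**The concern.** Anxiety and depression are scored as separate PROMIS-29 domains, so one hypothesis rests on two tests. At least four readings are open:

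- **Either domain suffices**, each tested at 0.05.
- **Both domains must differ.**
- **Each domain is a separate claim**, tested and interpreted alone.
- **The two T-scores are averaged** and tested once.

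The first exceeds the stated alpha. The second falls short of the stated power at the planned analysed size. The third and fourth can meet both, the fourth only if both domains change by about the planned amount.

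Both domains will be tested on any reading. What is left open is which result, or which combination, confirms the primary hypothesis. If that is settled after the data are seen, efficacy can be claimed on whichever domain happens to be significant.

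**Working it through.** **Inputs from section 7, Aim 1:** difference 5.5, SD 6, alpha 0.05, power 80%, 20 analysed and 25 recruited per arm, drop-out about 20%. **Assumed:** correlation r between the two T-scores of 0.5–0.8 (outer range 0–0.9), normal data, and, unless stated, 5.5 points and SD 6 in both domains.

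**1. The plan's own figure.** For one two-sample t-test at 20 per arm, the noncentrality is 5.5 / (6 × √(2/20)) = 2.90, with 38 df and two-sided critical value 2.024. Power is 80.6%. Solving for n gives 19.7, so 20 per arm, and 40 / 0.8 = 50 recruited. A one-sided 0.05 test would need only 16 per arm, so the calculation is two-sided. It reproduces, for one test.

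**2. Either rule and both rule.** The either-rule error is 1 − P(neither test rejects). With independent domains this is 1 − 0.95² = 9.75% two-sided, and 1 − 0.975² = 4.9% counting only results that favour iCBT. The power of the both rule is P(both tests reject in favour of iCBT). With correlated domains I simulated pairs of pooled t-tests, with at least 2,000,000 trials per setting:

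| r | Either: two-sided error | Either: error favouring iCBT | Both: power, 20/arm | Both: power, 25/arm |
|---|---|---|---|---|
| 0 | 9.8% | 4.9% | 65% | 79% |
| 0.5 | 9.1% | 4.6% | 69% | 81% |
| 0.7 | 8.4% | 4.2% | 72% | 83% |
| 0.8 | 7.9% | 3.9% | 74% | 84% |
| 0.9 | 7.1% | 3.5% | 76% | 85% |

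The error favouring iCBT is 3.9/2.5 ≈ 1.6 to 4.6/2.5 ≈ 1.8 times nominal at r 0.8–0.5. The either rule does not lack power: 88–92% at 20 per arm over the same range.

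**3. Size needed for the both rule.** Reaching 80% takes 25, 24 or 23 analysed per arm at r = 0.5, 0.7 or 0.8. From 25 recruited per arm, that tolerates drop-out of 0%, 4% (1/25) or 8% (2/25). At 20% drop-out, recruitment per arm is 25/0.8 → 32, 24/0.8 = 30, or 23/0.8 → 29, a total of 64, 60 or 58.

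**4. Holm's procedure at 20 per arm.** The smaller p-value is tested at 0.025 and, if it passes, the other at 0.05. For r = 0.5 to 0.8, two-sided familywise error is 4.7–4.1%, and 2.3–2.0% favouring iCBT. Power for at least one domain is 86%, 82% and 80% at r = 0.5, 0.7 and 0.8 (78% at 0.9). Power for both is 68–72%. If the second domain changes by only 2.75 points or not at all, power for at least one is 71–73%.

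**5. Mean of the two T-scores.** Its SD is 6 × √((1 + r)/2), which is 5.20 at r = 0.5 and 5.69 at r = 0.8. Power at 20 per arm is 90% and 85% if both domains change by 5.5 points, but 37% and 32% if only one does (a mean difference of 2.75).

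**The case against.** The strongest reply is that the plan states neither an either rule nor a both rule, so both failures belong to rules it never adopted. Read plainly, section 7 tests and reports each domain, the 'and' in Aim 1 supports this, and a separate test of each domain fits the sample size exactly. That reading is available. It does not say what confirms the single distress hypothesis when one domain is significant and the other is not, and the and/or wording lets either one do so. The Aim 1 sentence is a prediction, and it cannot serve as the success rule while it also includes a secondary outcome.

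Three points of emphasis stand:

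- The hypothesis is directional, so the relevant error is 3.9–4.6% against 2.5%, an excess of about 1.4–2.1 percentage points. About half of the two-sided 7.9–9.1% would favour mood tracking.
- The 20% drop-out is an allowance. If all 25 per arm are analysed, the both rule reaches 81–84%.
- The correlation and the unequal-effect cases are assumptions. Section 7 does say "The minimum clinically significant change in the domains of anxiety and depression has been shown to be 2.3-5.5 points", a range that contains 2.75, but that is a threshold of importance and not an expected effect.

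None of these supplies the missing rule, and the direction of the result holds for every r from 0 to 0.9.

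**Conclusion.** The concern holds, and it should be fixed before outcome data are examined because it decides whether the trial is called positive. At the 40 analysed participants the plan relies on, neither the either rule nor the both rule delivers both the stated 0.05 and the stated 80%. The either rule has a 3.9–4.6% chance of a false claim for iCBT (outer range 3.5–4.9%), and the both rule has 69–74% power (outer range 65–76%). These figures rest on an assumed correlation of 0.5–0.8, t-tests on normal data, and 5.5 points with SD 6 in each domain. A smaller effect in either domain would lower the both-rule power further. That the rule is missing rests on no assumption.

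**What to change.** Do one of the following, and align the Aim 1 wording in section 2 with it.

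1. **Name one domain as the single primary endpoint**, tested once at two-sided 0.05, with the other domain secondary. This is a wording change only: 40 analysed, 50 recruited and 80% power all stand. The price is that a benefit confined to the other domain is a secondary finding, and that power is 29% if the named domain's true difference is 2.75 points.

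2. **Keep both domains as primary under Holm's procedure**, say that the claim is for at least one domain, and restate the power. No added participants are needed if both domains change by 5.5 points and r is no more than about 0.8. If the second effect is half that size or nil, 80% power needs 24 analysed per arm, which is 60 recruited at 20% drop-out, 10 more than planned.

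If the sponsor wants both domains to be required, no alpha adjustment is needed, but 80% power at 20% drop-out takes 58–64 recruited. A prespecified mean of the two T-scores is also possible, but it loses much of its power if only one domain responds.

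### Perceived stress and HRQoL are defined as change but hypothesised and tested as scores, so the plan does not settle which quantity is compared between arms

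*Combined protocol and SAP*

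**What the plan says.** All the analysis text is in Section 7, Data Analysis, Aim 1.

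- Definition of the secondary outcomes: "Secondary outcomes will be the change in perceived stress, overall HRQoL and IBD disease activity".
- Hypotheses, two paragraphs later: "Our secondary hypotheses are that participants in the iCBT group will have lower perceived stress scores and higher HRQoL". No time point is named and change is not mentioned.
- Test: "To test these hypotheses, we will again use Student's t-test if the normality assumption is met or the Mann-Whitney U test" (the latter if normality is appreciably violated). There is no baseline term.
- Primary analysis, to which the word *again* refers back: the outcome is a level of distress "at 84 weeks between study arms", and the hypothesis is "lower psychological distress scores compared to those in the digital mood tracking group post-intervention". Definition and hypothesis agree here; both are levels.
- Disease activity: Aim 1 in Section 2 predicts "lower disease activity, as measured by patient-reported disease activity indices" with iCBT. In the Section 7 analysis text it appears only as a baseline predictor of T-score response ("we hypothesize that elevated disease activity at baseline"). No between-arm comparison of disease activity is given.

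**The concern.** The plan uses *level* for the primary outcome and *change* for the secondary ones, so it appears to distinguish the two. It then carries the primary test over to perceived stress and HRQoL with hypotheses worded as scores. An analyst could compare follow-up scores and cite the hypothesis and test sentences, or compare change scores and cite the outcome definition. Either could be presented as the planned analysis.

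In one trial of about 40 evaluable patients the two are not the same test. Chance baseline differences between arms enter the change score fully and enter the follow-up comparison only through the baseline-to-follow-up correlation. The two can therefore differ in power and in verdict, and an open choice between them inflates the false-positive rate. The results concerned are HRQoL, which is part (b) of Aim 1, and perceived stress, which belongs to part (a).

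**Working it through.** **1. The plan's own figure.** The sample size concerns the primary outcome: "Assuming a minimum clinically significant change of a 5.5 points difference in T-scores between study groups", SD 6, 80% power, alpha 0.05. The normal approximation gives 2 × (1.960 + 0.842)² × 6² / 5.5² = 18.7, so 19 per arm. The t-based calculation gives 19.7, so 20 per arm with power 80.6%. With dropout, 40 / (1 − 0.20) = 50. The stated 40 and 50 reproduce as a two-sided test; a one-sided test would need 15 per arm. No figure is given for any secondary outcome.

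**2. Inputs for the comparison.**
- From the documents: 20 evaluable per arm; SD 6; differences of 5.5 and 2.3 points (the ends of the stated range of minimum clinically significant change). The SD and differences belong to the primary scores and are borrowed here. They correspond to 5.5/6 = 0.92 SD and 2.3/6 = 0.38 SD. The midpoint, 3.9 points, is 0.65 SD.
- Assumed: equal SDs at both times and a baseline-to-follow-up correlation r of 0.3 to 0.8.

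**3. Formulas.**
- SD of change = 6 × √(2(1 − r)).
- Correlation between the two estimates of the arm difference = √((1 − r)/2).

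**4. Results.** 40,000 simulated trials per setting, two-sided 0.05, t-test on follow-up score and t-test on change in the same data. Power for change is the analytic value; repeat runs moved the simulated entries by about half a percentage point at most.

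| r | SD of change | Correlation of estimates | Power at 5.5: follow-up / change | No effect: at least one significant | Verdicts differ: no effect | 2.3 points | 3.9 points | 5.5 points |
|---|---|---|---|---|---|---|---|---|
| 0.3 | 7.10 | 0.59 | 81% / 67% | 8.7% | 7.5% | 20.9% | 31.5% | 27.1% |
| 0.5 | 6.00 | 0.50 | 81% / 81% | 9.3% | 8.4% | 24.6% | 33.4% | 22.4% |
| 0.7 | 4.65 | 0.39 | 81% / 95% | 9.3% | 8.7% | 32.5% | 39.1% | 19.9% |
| 0.8 | 3.79 | 0.32 | 81% / 99% | 9.5% | 9.0% | 40.5% | 44.1% | 19.5% |

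The two tests have equal power at r = 0.5. Change is weaker below that and stronger above it.

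**5. The baseline-adjusted alternative.** Write follow-up = a + τ·arm + b·baseline + error. Subtracting baseline from both sides gives change = a + τ·arm + (b − 1)·baseline + error. The arm effect τ and its standard error are the same either way, so the choice disappears.

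Relative to a follow-up variance of 1, the residual variance is 1 − r² = (1 − r)(1 + r). This never exceeds 1, nor 2(1 − r), the variance of change. At r = 0.3 the three values are 0.91, 1 and 1.40; at r = 0.8 they are 0.36, 1 and 0.40 (adjusted, follow-up, change). The cost is one degree of freedom, 37 instead of 38. In simulation at 0.8 SD, power was 72% adjusted against 69% (follow-up) and 55% (change) at r = 0.3, and 98% against 70% and 97.5% at r = 0.8. In every setting run, the adjusted model had at least the power of either unadjusted test.

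**The case against.** The best defence is that the sentences do different jobs. The outcome definition names the quantity (change), the hypothesis gives the direction, and the test sentence gives the method. Both named tests can be run on change scores, and *again* may carry over only the choice of test. That stands in part: the plan does not state two rival analyses, and the follow-up reading is an inference from *again* and from the primary wording. But the same argument concedes that the text permits either reading.

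Two further objections stand as limits on the claim. Both tests target the same mean difference, and significant results in opposite directions were essentially absent (at most 0.02% of trials). The 9% figure arises only if both tests are run and the better one is reported, which nothing in the plan proposes.

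A reader might infer more than the documents support:
- *That every secondary conclusion is affected.* Disease activity has no between-arm test in Section 7, as change or as follow-up score, so there is no such mismatch for it.
- *That the two analyses would usually contradict each other.* In every setting run they agree in most trials, and at the larger correlations much of the disagreement is simply the power gap.
- *That the trial's main result is in doubt.* The primary outcome is a level at follow-up in both its definition and its hypothesis.

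**Conclusion.** The point holds for perceived stress and overall HRQoL: the plan does not say whether change or follow-up score is compared. The consequence is loss of precision under one reading or the other and room for a post-hoc choice; the quantity being estimated does not differ.

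At 20 per arm, choosing the better test takes type I error to about 9%, a figure that hardly moves with r. Verdicts differ in about 8-9% of trials with no effect, in about 20-41% at 0.38 and 0.92 SD, and in up to 44% at 0.65 SD. These figures assume equal SDs, r between 0.3 and 0.8, and the primary outcome's SD and effects applied to the secondary scales. They were obtained with t-tests; the Mann-Whitney branch was not simulated. Since the affected outcomes are secondary and unpowered, this is a clarification worth making before the data are analysed and no threat to the trial's main conclusion.

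**What to change.** In Section 7, replace the secondary t-test/Mann-Whitney sentence for perceived stress and HRQoL with one linear model per outcome: follow-up score on arm and the baseline value of the same score, reporting the arm difference with its 95% confidence interval. Reword the outcome definition to match. This replaces the existing test sentence, because a baseline-adjusted model is neither of the tests now named. The non-normality fallback must therefore be rewritten too, for example as a named sensitivity analysis. If the sponsor prefers an unadjusted test, name either change or follow-up score and use it in both places.

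The cost is a short text amendment. No visit, patient or data item is added: Table 1 already collects PROMIS-29 and the Perceived Stress Scale at baseline and follow-up.

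Do not extend the model to disease activity as things stand. It first needs a stated between-arm analysis. Table 1 also collects the Simple Clinical Colitis Activity Index for ulcerative colitis, whereas Section 7 names Mayo sub-scores, and the two must be reconciled. Crohn's disease and ulcerative colitis use different indices, so a single model of one score would not cover all participants.
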